All patients who received anticancer therapy will be included in the toxicity and safety analysis. Incidence tables will be generated to summarize incidence of patients reporting at least one episode of each specific AE, the incidence of AE causing withdrawal from the study and incidence of SAE. The total number of episodes for each event reported (Frequency Table), the severity and attribution to study therapy of each episode reported (Severity Table and Attribution Table) will also be evaluated.

Subjects receive treatment on the recommended regimens for as long as the treating oncologist feels they are benefiting from the treatment, and the patient wishes to continue. Subjects will be followed until disease progression.

Attachments

Attach Type	File Name
StudyDesign	Attachment_Treatment plan schema.pdf

Subject Recruitment Methods & Advertising

Describe how the study team will identify and recruit subjects. Please consider the following items and provide additional information as needed so that the IRB can follow each step of the recruitment process.

- How will the study team identify potential participants?
- Who will first contact the potential subjects, and how?
- Will you use advertisements? If so, how will you distribute those?
- How and where will the research team meet with potential participants?
- If applicable, describe proposed outreach programs for recruiting women, minorities, or disparate populations.
- How you will minimize undue influence in recruitment?

- Attach copies of all recruiting and advertising materials (emails, verbal scripts, flyers, posts, messages, etc.).

For additional information on recruiting and advertising:

- [IRB Application Instructions - Advertisements](#)
- [PI Guide to Identification and Recruitment of Human Subjects for Research](#)

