6. STUDY DESIGN AND STATISTICAL CONSIDERATIONS

6.1 Study Design and Endpoints

This is a single-arm, pilot trial in patients with metastatic high grade large cell neuroendocrine carcinoma (HG-LCNEC) to study the feasibility of upfront NGS directed treatment in high grade neuroendocrine carcinomas. Tumor samples will receive next generation sequencing (NGS) profiling to classify the tumor as: small cell-like or non-small cell-like. Non-typeable cases will not be eligible for participation in this study, neither is small cell neuroendocrine carcinoma (HG-SCNEC). The systemic therapy regimen will be determined based on the NGS profile of the tumor.

Feasibility is defined as being able to sequence the patient within 2 months of initial medical oncology visit and being able to assign into molecularly-defined cohorts (TP53 and RB1 co-mutated vs non-co-mutated).

Secondary outcomes include ORR and progression-free survival (PFS). Radiological response will be assessed via RECIST Version 1.1 criteria (Appendix B) based on standard-of-care CT scans completed at q2 monthly intervals during treatment and q3 month during observation. PFS is defined from date of on study to the date of disease progression or death or date of last follow-up whichever occurs first. PFS will be assessed via standard-of-care CT scans (q2 month intervals during active treatment and q3 months during observation) as graded by RECIST Version 1.1 criteria for up to one year post-study enrollment.

All patients who received anticancer therapy will be included in the toxicity and safety analysis. Incidence tables will be generated to summarize incidence of patients reporting at least one episode of each specific AE, the incidence of AE causing withdrawal from the study and incidence of SAE. The total number of episodes for each event reported (Frequency Table), the severity and attribution to study therapy of each episode reported (Severity Table and Attribution Table) will also be evaluated.

Listings of AEs by patients will include the following information: time to onset, the duration of each AE, the severity of each AE, the relationship of the AE to study therapy, whether it was a serious AE (or not), and whether the AE caused withdrawal. Toxicities will be graded according to Common Toxicity Criteria (CTCAE) v5.

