6.2 Sample Size/Accrual Rate

We plan to enroll 15 patients on this pilot trial to study the feasibility of upfront NGS directed treatment in high grade neuroendocrine carcinomas and evaluate the ORR and progression-free survival.

Feasibility is defined as being able to sequence the patient within 2 months of initial medical oncology visit and being able to assign into molecularly defined cohorts (TP53 and RB1 co-mutated vs non co-mutated). If more than 50% patients are not able to sequence within 2 months

of initial medical oncology visit or more than 50% patients are not able to assign into molecularly defined cohorts, the study will be deemed not feasible. No stopping rule is planned to stop enrollment based on feasibility. With 15 patients, the probability of unfeasible of the study is calculated with true unfeasibility probability p from 0.2 to 0.8 (Table 1). From this calculation we see if the true unfeasibility rate <0.5 , the probability to declaim the trial unfeasible is low and if the true unfeasibility rate >0.5 , the probability to declaim the trial unfeasible is high.

Table 1: Probability of unfeasibility for this pilot study

True prob. of unfeasible	$p=0.2$	$p=0.3$	$p=0.4$	$p=0.5$	$p=0.6$	$p=0.7$	$p=0.8$
Prob. of unfeasible	0.0042	0.050	0.213	0.50	0.787	0.950	0.996

The expected accrual rate is about 8 patients per year and accrual duration is approximately 2 years, with an additional 1 year follow-up after the last patient is enrolled on the study for observation of disease progression. Thus, the total study duration is about 3 years.

All patients who completed at least 2-cycle treatments will be evaluable for the ORR objective. Patients who fail to complete 2-cycles of the treatment due to toxicity or withdrawal from study will be excluded from the ORR evaluation. All patients enrolled on the study will be evaluable for the PFS.

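### The Severity and Attribution Tables count AE episodes, so no planned summary table gives the number of treated patients with grade 3 or higher, or treatment-related grade 3 or higher, toxicity

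*Combined protocol and SAP*

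**What the plan says.** The safety paragraph appears twice in the same terms: in the Study Design part of the Research Description and in section 6.1.

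- **Population.** "All patients who received anticancer therapy will be included in the toxicity and safety analysis". Section 6.2 sets enrolment: "We plan to enroll 15 patients on this pilot trial to study the feasibility of upfront NGS directed treatment". The safety denominator is therefore at most 15.
- **Patient-level tables.** "Incidence tables will be generated to summarize incidence of patients reporting at least one episode of each specific AE", followed by "the incidence of AE causing withdrawal from the study and incidence of SAE". The unit of the withdrawal and SAE items is not spelled out; because they sit under the incidence tables, I read them as patient counts. None of these tables is split by grade or by attribution.
- **Episode-level tables.** In section 6.1, "The total number of episodes for each event reported (Frequency Table), the severity and attribution to study therapy of each episode reported"; in the Study Design part, likewise, "the severity and attribution to study therapy of each episode reported (Severity Table and Attribution Table) will also be evaluated". This covers the Frequency, Severity and Attribution Tables.
- **Listings.** Section 6.1 alone adds by-patient output: "Listings of AEs by patients will include the following information". The items are onset, duration, severity, relationship to study therapy, seriousness and whether the event caused withdrawal. Grading is by CTCAE v5.
- **Exposure.** "Subjects receive treatment on the recommended regimens for as long as the treating oncologist feels they are benefiting", provided that the patient also wishes to continue.

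Section 6.4, which sets out the endpoint analyses, contains no safety summary.

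**The concern.** Grade and attribution are what turn an AE count into a statement about tolerability, and the plan summarises them only over episodes. Episodes within a patient are not independent. Treatment has no fixed length, so patients who stay on longer have more opportunity to contribute episodes. A table of graded episodes therefore mixes how many patients were affected with how often each one had the event recorded.

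Severity and attribution are also named as two separate tables, and no cross-classification is described. Even at episode level, the number that were both grade 3 or higher and attributed to study therapy would not follow from them.

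SAE incidence does not fill the gap. Seriousness, grade and relationship are different attributes, and the section 6.1 listing treats them as separate items.

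At stake is whether a reader of the summary tables can tell how many of the treated patients had severe, or severe and related, toxicity.

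**Working it through.** The plan states no safety figure to reproduce. Its only computed figures are in Table 1 of section 6.2. The exact probability P(X ≥ 8) for X ~ Binomial(15, p) matches all seven entries (0.0042 at p = 0.2, 0.500 at p = 0.5, 0.996 at p = 0.8). That table concerns feasibility and has no bearing here. The check is on the unit of each planned output, followed by an illustration.

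**Step 1. Unit of each planned output**

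| Output | Unit | Grade? | Attribution? |
|---|---|---|---|
| Incidence of each AE | patient | no | no |
| AEs causing withdrawal; SAEs | patient (as read) | no | no |
| Frequency Table | episode | no | no |
| Severity Table | episode | yes | no |
| Attribution Table | episode | no | yes |
| By-patient listing (6.1) | each AE, within patient | yes | yes |

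No summary table has the patient as its unit together with grade or attribution. Only the listing carries all three.

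**Step 2. What the tables together imply for one event**

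Let E be the grade 3 or higher episodes (Severity Table), T all episodes (Frequency Table), m the patients with the event at any grade (incidence table), and k the patients with at least one grade 3 or higher episode, with E ≥ 1.

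- Upper bound: k ≤ min(E, m).
- Lower bound: each of the m − k patients without a severe episode needs at least one of the T − E lower-grade episodes, so k ≥ max(1, m − (T − E)).

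**Step 3. Numbers**

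The documents give no toxicity rates, so the counts are assumed: 15 treated patients and E = 7.

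- Lowest: k = 1, 1/15 = 6.7%, exact (Clopper-Pearson) 95% CI 0.2% to 31.9%.
- Highest: k = 7, 7/15 = 46.7%, exact 95% CI 21.3% to 73.4%.

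The top of the range requires m ≥ 7. With m = 7, the bottom also requires at least 7 − 1 = 6 lower-grade episodes, one in each of the other patients. If m = 2, k can only be 1 or 2. If no lower-grade episodes were recorded (T = E), k = m exactly. The planned tables thus sometimes narrow the answer and sometimes leave the whole range open.

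**Step 4. One patient with many episodes**

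Assume that one patient has 10 severe episodes and five others have one each. The Severity Table total is 10 + 5 = 15 severe episodes, of which 10/15 = 67% belong to one patient. The patients affected number 6/15 = 40% (exact 95% CI 16.3% to 67.7%).

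**Step 5. All events together, and related events**

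The bounds in Step 2 apply to one AE term at a time. The incidence tables are described per specific AE, and patients overlap between terms, so the number with any grade 3 or higher AE cannot be obtained by adding rows. For related severe episodes, with A the episodes attributed to study therapy, the two separate tables fix the joint count only to between max(0, E + A − T) and min(E, A), and that is still a count of episodes.

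**The case against.** The strongest reply is that nothing is lost. The section 6.1 listings put grade and relationship in the same by-patient record, and with at most 15 patients anyone holding the listing can count those with severe or related severe events. This stands. A reader might infer that the patient-level figure will be unobtainable; the documents do not support that. It is only absent from the summary tables, and a listing sets no worst-grade rule, denominator or interval.

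A reader might also take the range of 1 to 7 patients as always unresolved. It is not, because the any-grade incidence of the same event caps it, as Step 2 shows.

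A further inference would be that severe toxicity will be diluted by mild repeats. For example, with five mild episodes in each of 12 patients and one severe episode in each of 3, severe episodes are 3/(12 × 5 + 3) = 3/63 = 4.8%, against 3/15 = 20% of patients. That assumes severity will be displayed as a percentage of episodes, which the plan never says. A plain count would show 3 severe episodes, hence at most 3 patients.

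Finally, safety is not among the listed objectives, no decision or stopping rule uses these tables, and the Research Procedures part describes assigned regimens as currently FDA-approved and NCCN-recommended. A pooled rate across differing regimens in so few patients would be imprecise and hard to interpret. This limits the importance of the point. It does not make the episode the better unit for tables the plan has already committed to produce.

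**Conclusion.** The point holds as a minor one. In both places the plan makes the episode the unit for severity and attribution, and no summary table gives treated patients with grade 3 or higher, or related grade 3 or higher, toxicity. The gap can be as wide as 1/15 to 7/15 for one event with 7 severe episodes. That range rests on assumed counts and narrows whenever the incidence or Frequency Table constrains it.

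The conclusion depends on reading the words about each episode literally and on the withdrawal and SAE summaries not being split by grade or attribution, which the text supports. It does not mean that safety data are missing, that severe toxicity will be understated, or that any study conclusion is at risk. Feasibility, ORR and PFS are unaffected.

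**What to change.** Make the same change in the Study Design part of the Research Description and in section 6.1:

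- Make the patient the unit of the Severity Table: number and percent of treated patients by worst CTCAE v5 grade, overall and per AE term.
- Make the patient the unit of the Attribution Table: number and percent of treated patients by worst grade among AEs attributed to study therapy, overall and per AE term.
- Give an exact 95% CI for two overall rows only: any grade 3 or higher AE, and any related grade 3 or higher AE. Intervals for every AE term are not needed.
- Keep the episode counts as a supplement.

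The cost is a few lines of text and one extra summary, programmed from fields the by-patient listing already contains. No new data collection and no change to sample size or conduct is required. With at most 15 patients the intervals will be wide, and the report should say so.

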Screening shall include: complete history; physical examination and evaluation of ECOG (Eastern Cooperative Oncology Group) Performance Status; histopathological confirmed diagnosis of high grade neuroendocrine carcinoma; CBC; serum chemistries and baseline computerized tomographic (CT) scan (within 6 weeks of starting treatment) for RECIST 1.1 evaluation. Baseline lab tests and radio-graphic studies should be completed within 6 weeks prior to registration/initiation of treatment. All of these are standard of care for metastatic carcinoma of HG-NEC type.

The case will be reviewed at MTB once the NGS report is ready, patient meets inclusion criteria and has consented to participate in the study. The MTB will provide a written review of the molecular sequencing of the subject, and the study statistician will review and assign subjects to cohorts, in consultation with the PI. Subjects will be assigned to the current FDA-approved, NCCN-recommended treatment regimen based on their molecular profile and will continue treatment for as long as the risk-benefit profile remains favorable, the study remains active, and they wish to continue.

All the procedures to be carried out are illustrated in the attached study calendar. All the tests/procedures are standard of care for this patient population.

Attachments

Attach Type	File Name
ResearchProcedures	Study Calander.pdf

Data Collection & Research Materials

In this section, please provide the following:

- Describe all sources or methods for obtaining research materials about or from living individuals (such as specimens, records, surveys, interviews, participant observation, etc.), and explain why this information is needed to conduct the study.
- For each source or method described, please list or attach all data to be collected (such as genetic information, interview scripts, survey tools, data collection forms for existing data, etc.).
- If you will conduct a record or chart review, list the beginning and end dates of the records you will view.

This study has no data collection instruments.

Attachments**Resources**

Describe the availability of the resources and adequacy of the facilities that you will use to perform the research. Such resources may include:

- Staffing and personnel, in terms of availability, number, expertise, and experience;
- Computer or other technological resources, mobile or otherwise, required or created during the conduct of the research;

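### Cohort assignment, one of the two primary feasibility criteria, is made by the study statistician with the PI; the tumor board should record it, with not-assignable patients kept in the denominator

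*Combined protocol and SAP*

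**What the plan says.** The Research Procedures section splits the work in two. First, "The MTB will provide a written review of the molecular sequencing of the subject". Then "the study statistician will review and assign subjects to cohorts, in consultation with the PI". The text does not ask the MTB to state a cohort.

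Section 6.2 makes assignability one of two feasibility criteria, beside sequencing within 2 months. On this criterion the rule is that if "more than 50% patients are not able to assign into molecularly defined cohorts, the study will be deemed not feasible". Section 6.4 estimates the percentage assigned and names no source document, reader or check for it.

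The cohorts are TP53 and RB1 co-mutated versus not co-mutated, read from the sequencing panel (sections 6.1 to 6.3). The Study Design section lists a third result, non-typeable. Section 6.1 omits it from the list of classes, but both sections make such cases ineligible. Neither defines it.

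On treatment, section 6.1 says: "The systemic therapy regimen will be determined based on the NGS profile of the tumor".

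**The concern.** Whether a patient counts as assigned is an outcome. Here study personnel decide it in an open, single-arm trial of 15, and whoever makes the successive assignments knows the earlier ones. Clear TP53/RB1 results leave no room for judgement. An ambiguous result might, because non-typeable has no written definition and criterion 3.1.2 accepts prior CLIA-certified reports, so reports may not be uniform.

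The same judgement acts twice. Calling a patient assignable adds to the numerator. Calling a patient non-typeable makes that patient ineligible, which can remove the patient from the denominator. The documents do not name who makes the non-typeable call; the natural reading is that it belongs to the assignment step. At stake is the credibility of one primary percentage, and, in a narrow range of results, the feasibility verdict.

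**Working it through.** **Inputs.** n = 15 (section 6.2). Not feasible on this criterion if more than 50% cannot be assigned, that is 8 or more of 15 (section 6.2). True unfeasibility rates p from 0.2 to 0.8 (Table 1). Expected cohorts of 6 and 9 (section 6.3). Published series of 45 tumors: 18 small cell-like, 25 non-small cell-like, 2 carcinoid-like (Background).

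**Step 1: reproduce Table 1.** With X the number of failures, X ~ Binomial(15, p), the table should be P(X ≥ 8). This gives 0.0042, 0.0500, 0.2131, 0.5000, 0.7869, 0.9500 and 0.9958, which agrees with the printed 0.0042, 0.050, 0.213, 0.50, 0.787, 0.950 and 0.996. The table treats one criterion at a time.

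**Step 2: effect of one relabelled patient.** The percentage moves by 1/15 = 6.7 points. If one unassignable patient is counted as assigned, 9 true failures are needed for a not-feasible verdict instead of 8. The verdict changes only when X = 8, with probability P(X = 8) = 6435 × p^8 × (1 − p)^7.

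| p | P(X ≥ 8) | P(X ≥ 9) | P(X = 8) |
|---|---|---|---|
| 0.2 | 0.0042 | 0.0008 | 0.0035 |
| 0.3 | 0.0500 | 0.0152 | 0.035 |
| 0.4 | 0.2131 | 0.0950 | 0.118 |
| 0.5 | 0.5000 | 0.3036 | 0.196 |
| 0.6 | 0.7869 | 0.6098 | 0.177 |
| 0.7 | 0.9500 | 0.8689 | 0.081 |
| 0.8 | 0.9958 | 0.9819 | 0.014 |

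The last column is computed from unrounded values. These figures assume that one failure is relabelled and that the 2-month criterion passes. They do not predict that a relabelling will occur.

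**Step 3: which p is plausible.** Section 6.3 expects 6 + 9 = 15, so no unassignable patients. In the cited series 18 + 25 = 43 of 45 fell into the two major cohorts and 2/45 = 4.4% did not; at that rate P(X = 8) is about 7 × 10⁻⁸. The 4.4% is only a rough stand-in, since those two tumors were a separate class and are not said to lack a TP53/RB1 result. The region where relabelling matters, p of about 0.4 to 0.6, has no support in the documents.

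**Step 4: the denominator.** Suppose 15 patients are assigned and k others are called non-typeable (k is an illustration, not a figure from the plan). If those k are dropped as ineligible, the percentage is 15/15 = 100% whatever k is. If they are kept, it is 15/(15 + k): 93.8% for k = 1 and 88.2% for k = 2. The verdict would change only if k exceeded 15. So the exclusion affects the reported percentage more readily than the verdict.

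**The case against.** The strongest reply is that little discretion exists. The MTB reviews every case and issues its written review before assignment, and nothing in the text lets the statistician override it. The cohorts are a stated two-gene dichotomy. Since non-typeable cases are ineligible, nearly every enrolled patient will be assigned whoever does the assigning, so the exclusion weakens the endpoint more than the identity of the assigner does. All of this stands, and it is why the effect is judged small. It does not remove the point, because the exclusion is itself a result of the ambiguous call.

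It is also fair that moving the call to the MTB without defining not assignable would only relocate the judgement, and that MTB membership is not given, so its independence from the PI is not shown. The fix therefore needs the written definition and the denominator rule as well. Finally, the IRB application lists a full protocol (Amendment 1) and a treatment schema as attachments, and only section 6 of the protocol is available here. A classification rule may exist in the rest.

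A reader might infer that those who report feasibility decide its successes. The documents do not say who reports feasibility, and the 2-month criterion does not depend on the assigners. A reader might also infer that a treatment-determining call is taken away from the MTB. The documents tie the regimen to the molecular or NGS profile, not to the statistician's cohort label, so this is not supported either.

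**Conclusion.** The point holds as a modest, avoidable weakness in how a primary criterion is recorded. Study personnel aware of earlier assignments make the call, no written rule covers ambiguous tumors in the available text, and the call can affect both parts of the percentage. One relabelled patient is worth 6.7 points. The chance that this changes the verdict peaks near 0.2 when the true unassignable rate is about 50%, and is 0.0035 at 0.2, the lowest rate in Table 1. A reader might take the peak as the risk in this trial; the non-typeable exclusion, the expected 6 + 9 split and the cited series all point to a much lower rate. The conclusion rests on reading the non-typeable call as part of the assignment step, and on there being no classification rule in the unseen parts of the protocol.

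**What to change.** Replace the assignment clause in Research Procedures with wording such as: The MTB records in its dated written review one of three categories: TP53/RB1 co-mutated, not co-mutated, or not assignable, using a definition of not assignable written before enrollment. The study statistician tabulates the MTB category without altering it.

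In section 6.4, name that record as the source for the assignment percentage, and state that consented, sequenced patients recorded as not assignable count in its denominator. This concerns the feasibility count only and leaves eligibility for study treatment as it is. State also whether the planned 15 includes these patients, since Table 1 is calculated for a denominator of 15.

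The cost is one field on a review that the MTB already writes, a short definition, and a feasibility percentage that may come out slightly less favourable.
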